Appendix D: Postintervention provider interview guide

Introduction:

Thank you for your interest in this study. The aim of the interview is to help us understand your experiences implementing the AYA Needs Assessment and Service Bridge (NA-SB). During the interview, I will ask questions about NA-SB implementation including barriers you encountered and strategies you used.

Our discussion should last approximately one hour. All of your responses will remain confidential and will only be reported in aggregate. You may choose to stop the interview at any time, and there is no penalty to you or your organization for not completing the interview. Before we begin, we would like to ask your permission to audio record our discussion for the purposes of future analysis. Would it be OK with you if I record this interview? (*If participant refuses to be audio-recorded, the RA will take notes instead.*) The interview will be transcribed; however, your name or any personal identifiers will not be associated with any of the notes. The audio recordings will be deleted once the project is complete.

Do you have any questions before we begin?

Intervention Characteristics

Evidence Strength & Quality

1. In a healthcare setting, influential stakeholders may include influential and well-respected clinicians, where as in an education setting, this may include influential and well-respected teachers or educators.

What do influential stakeholders think of the intervention?

o What do administrative or other leaders think of the intervention?

Adaptability

- 1. What kinds of changes or alterations do you think you will need to make to the intervention so it will work effectively in your setting?
 - o Do you think you will be able to make these changes? Why or why not?

Complexity

- 1. How complicated is the intervention?
 - o Please consider the following aspects of the intervention: duration, scope, intricacy and number of steps involved and whether the intervention reflects a clear departure from previous practices.

Design Quality & Packaging

- 1. What is your perception of the quality of the supporting materials, packaging, and bundling of the intervention for implementation?
 - o Why?

Cost

1. What costs will be incurred to implement the intervention?

Outer Setting

Patient Needs & Resources

- 1. How well do you think the intervention will meet the needs of the individuals served by your organization?
 - o In what ways will the intervention meet their needs? E.g. improved access to services? Reduced wait times? Help with self-management? Reduced travel time and expense?
- 2. How do you think the individuals served by your organization will respond to the intervention?
- 3. What barriers will the individuals served by your organization face to participating in the intervention?
- 4. Have you heard stories about the experiences of participants with the intervention?
 - o Can you describe a specific story?

Inner Setting

Structural Characteristics

- 1. How will the infrastructure of your organization (social architecture, age, maturity, size, or physical layout) affect the implementation of the intervention?
 - o How will the infrastructure facilitate/hinder implementation of the intervention?
 - o How will you work around structural challenges?
- 2. What kinds of infrastructure changes will be needed to accommodate the intervention?
 - Changes in scope of practice? Changes in formal policies? Changes in information systems or electronic records systems? Other?
 - o What kind of approvals will be needed? Who will need to be involved?

o Can you describe the process that will be needed to make these changes?

Culture

- 1. How do you think your organization's culture (general beliefs, values, assumptions that people embrace) will affect the implementation of the intervention?
 - o Can you describe an example that highlights this?

Implementation Climate

1. This question is likely to uncover topics to explore more within other sub-constructs, but be attentive to other themes that may not be included in your assessment.

What is the general level of receptivity in your organization to implementing the intervention?

o Why?

Compatibility

- 1. How well does the intervention fit with your values and norms and the values and norms within the organization?
 - Values relating to interacting with individuals served by your organization, e.g. shared-decision making vs. being more directive?
 - o Values related to referring to outside vendor-based programs vs. providing services by in-house staff?
- 2. How well does the intervention fit with existing work processes and practices in your setting?
 - What are likely issues or complications that may arise?
- 3. Can you describe how the intervention will be integrated into current processes?
 - o How will it interact or conflict with current programs or processes?

Goals & Feedback

1. This question can be framed in terms of the intervention. For example, in a healthcare setting: How does implementation of the intervention align with organizational goals related to preventing How does implementation of the intervention align with other organizational goals?

Readiness for Implementation

Leadership Engagement

- 1. What level of involvement has leadership at your organization had so far with the intervention?
 - o Do they know about the intention to implement the intervention?
 - o Who are these leaders? How do attitudes of different leaders vary?
 - What kind of support have they given you? Can you provide specific examples?
- 2. What kind of support or actions can you expect from leaders in your organization to help make implementation successful?
 - o Who are these leaders? How do attitudes of different leaders vary?
 - o Do they know about the intention to implement the intervention?
 - o What kind of support can you expect going forward? Can you provide specific examples?
 - o What types of barriers might they create?

Available Resources

- 1. Do you expect to have sufficient resources to implement and administer the intervention?
 - o [If Yes] What resources are you counting on? Are there any other resources that you received, or would have liked to receive?
 - What resources will be easy to procure?
 - o [If no] What resources will not be available?
- 2. How do you expect to procure necessary resources?
 - o Who will be involved in helping you get what is needed?
 - What challenges do you expect to encounter?

Characteristics of Individuals

Knowledge & Beliefs about the Intervention

1. What do you know about the intervention or its implementation?

Self-efficacy

- 1. How confident are you that you will be able to successfully implement the intervention?
 - What gives you that level of confidence (or lack of confidence)?
- 2. How confident do you think your colleagues feel about implementing the intervention?
 - o What gives them that level of confidence (or lack of confidence)?

Process

Planning

1. What have you done (or what do you plan to do) to get a plan in place to implement the intervention?

Engaging

Opinion Leaders

1. Who are the key influential individuals to get on board with this implementation?

Key Stakeholders

- 1. Who are the key individuals to get on board with the intervention?
 - o To encourage individuals to use the intervention? To help with implementation?

Intervention Participants

- 1. How will you or your colleagues communicate to the individuals that are served by your organization about the intervention?
 - How will they participate in the intervention?
 - o How will they access the intervention?

Reflecting & Evaluating

- 1. What kind of information do you plan to collect as you implement the intervention?
 - o Which measures will you track? How will you track them?
 - o How will this information be used?
- 2. How will you assess progress towards implementation or intervention goals?
 - o How will results of the evaluation be distributed to stakeholders?

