Referral pathway initiation. Within seven calendar days of AYA NA-SB completion, the implementation leader will review completed needs assessments and, depending on AYAs' preferences indicated at the end of the needs assessment, will either (a) initiate appropriate referral pathways, or (b) provide a list of recommended referrals to AYAs. For each needs assessment reviewed, they will document these actions on a brief fidelity checklist which timestamps their completion of these tasks, documents the referral pathways selected, and gauges their confidence in selecting appropriate referral pathways (**Appendix B**). This process is expected to take less than 10 minutes/ needs assessment.

Postintervention AYA survey. One month following their completion of the needs assessment, I will engage AYA pilot participants in an online postintervention survey (**Appendix C**) assessing their perceptions of AYA NA-SB's feasibility, acceptability, and appropriateness. In addition to items assessing AYAs' perspectives of the needs assessment itself, this survey will solicit information about the follow-up care AYAs received in response to needs they reported in the needs assessment and whether they felt their needs were met (Aim 2). This survey will administered through RedCAP and will take approximately 15 minutes to complete. AYAs will receive a second \$15 incentive for completing the postintervention survey.

Postintervention provider interview. I will conduct a semi-structured interview with the implementation leader and other participating providers from NCCH after AYA NA-SB has been administered to a minimum of n=15 AYAs. The purpose of this 1-hour interview is to assess provider perceptions of the feasibility, acceptability, and appropriateness of AYA NA-SB and to elicit information about perceived implementation determinants and strategies deployed. Interviews will be recorded and transcribed for analysis. **Appendix D** contains the interview guide.

Activity	Provider Training	Needs assessment administration	Referral pathway initiation	Postintervention AYA survey	Postintervention provider interview
Time	0	+6 weeks	+7 weeks	+10 weeks	+10-15 weeks

Instruments & procedure (Aims 3)

I will conduct annual semi-structured qualitative interviews with AYA providers and program leaders from diverse health systems to proactively address challenges and prepare for future AYA NA-SB scale-up and sustainability.

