An interview guide (**Appendix E**) was developed using domains and constructs from the Dynamic Sustainability Framework, which conceptualizes the dynamic relationship among interventions, practice settings, and broader systems over time. ¹⁹ During interviews, I will review pilot data with providers and ask them to consider how AYA NA-SB's implementation and outcomes might unfold similarly or differently in their health systems given their practice context (e.g., staffing, informational systems, culture) and broader context (e.g., policy, regulations, market forces).

I will conduct interviews via telephone at a time of participants' choosing. Interviews will last approximately 60 minutes. They will be recorded and transcribed for analysis.

Outcome Measure(s)

Variable	Definition	Measure	Participants	Data source				
Demographic/clinical variables (Aim 1, Aim 2)								
Demographics	Age; sex; race/ethnicity; healt	AYAs	Needs assessment					
Clinical	Cancer diagnosis; stage at dia	AYAs	Needs Assessment					
variables		_						
	Implementation measures (Aim 1)							
Feasibility	extent to which AYA NA-	Feasibility of Intervention Measure	AYAs	Postintervention				
	SB can be successfully used (FIM) ²⁰			AYA survey				

	in cancer programs		Providers	Postintervention provider interview
Acceptability	perception of whether AYA-NA-SB is agreeable,	Acceptability of Intervention Measure (AIM) ²⁰	AYAs	Postintervention AYA survey
	palatable, or satisfactory to users		Providers	Postintervention provider interview
Appropriateness	SB's fit, relevance, or Measure (IAM) ²⁰		AYAs	Postintervention AYA survey
	compatibility with the context in which it will be used		Providers	Postintervention provider interviews
Fidelity	the degree to which AYA NA-SB is implemented as intended	Proportion of needs assessment reviewed by provider within one week and referral pathways initiated	Providers	Fidelity checklist
Implementation determinants	Perceived barriers and facilitators to AYA NS-SB implementation	Qualitative analysis of perceived determinants based on CFIR constructs	Providers	Postintervention provider interview
Implementation strategies	Strategies deployed to facilitate AYA NA-SB implementation	Qualitative analysis of strategies used and their perceived level of influence	Providers	Postintervention provider interview
	Service	e and patient outcomes (Aim 2)		
AYA needs	variables(?)	crosstab with demographic/clinical	AYAs	Needs assessment

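### The postintervention provider interview guide asks mainly for expectations and current views: 16 of its 30 main questions are future-only, and none directly asks which barriers or facilitators were met

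*Combined protocol and SAP*

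**What the plan says.** Instruments & procedure (Aims 1,2) has the investigator interview the implementation leader and "other participating providers from NCCH after AYA NA-SB has been administered to a minimum of n=15 AYAs". The interview is to assess provider views of feasibility, acceptability and appropriateness, and "to elicit information about perceived implementation determinants and strategies deployed". The schedule in that section puts needs assessment administration at +6 weeks and this interview at +10 to +15 weeks.

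The Outcome Measure(s) table defines implementation determinants as "Perceived barriers and facilitators to AYA NS-SB implementation", measured by "Qualitative analysis of perceived determinants based on CFIR constructs". The provider interview is the only data source listed for that outcome. It is also the only provider source for feasibility, acceptability and appropriateness.

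The introduction to Appendix D tells the provider that the interview covers "NA-SB implementation including barriers you encountered and strategies you used". The questions that follow include:

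- Adaptability: "What kinds of changes or alterations do you think you will need to make to the intervention"
- Patient Needs & Resources, item 3: "What barriers will the individuals served by your organization face to participating in the intervention"
- Self-efficacy, item 1: "How confident are you that you will be able to successfully implement the intervention"

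**The concern.** The timing, purpose and introduction of the interview all point to what happened in the pilot. Many of the questions read as if the site had not yet started.

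This matters because expectations are already available from elsewhere. Under Interventions and Interactions, development work has produced a list of possible barriers, and the third hour of provider training is given to brainstorming strategies. What the pilot can add is knowledge of which barriers and facilitators actually arose. If the interview does not ask for that plainly, the determinants reported under Aim 1 will rest partly on forecasts.

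The coding would not separate the two. The Analytical Plan describes template analysis by implementation outcome and CFIR construct, with room for emergent themes, but no distinction between anticipated and experienced determinants. An expected barrier and an encountered one could be filed under the same construct with nothing to tell them apart.

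**Working it through.** The documents give no count of questions and no formula applies, so the check is a classification. Each numbered main question in Appendix D was classed by its own wording, without its probes, as future only, present perception, experience to date, or mixed.

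| Construct group | Main questions | Future only | Present | To date | Mixed |
|---|---|---|---|---|---|
| Intervention Characteristics | 5 | 2 | 3 | 0 | 0 |
| Outer Setting | 4 | 3 | 0 | 1 | 0 |
| Inner Setting, including Readiness | 12 | 7 | 4 | 1 | 0 |
| Characteristics of Individuals | 3 | 1 | 2 | 0 | 0 |
| Process | 6 | 3 | 2 | 0 | 1 |
| Total | 30 | 16 | 11 | 2 | 1 |

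- **Future only (16):** Adaptability; Cost; Patient Needs & Resources 1, 2 and 3; Structural Characteristics 1 and 2; Culture; Compatibility 3; Leadership Engagement 2; Available Resources 1 and 2; Self-efficacy 1; Intervention Participants; Reflecting & Evaluating 1 and 2.
- **Present (11):** Evidence Strength & Quality; Complexity; Design Quality & Packaging; Implementation Climate; Compatibility 1 and 2; Goals & Feedback; Knowledge & Beliefs; Self-efficacy 2; Opinion Leaders; Key Stakeholders.
- **To date (2):** Patient Needs & Resources 4 (stories heard about participants); Leadership Engagement 1 (involvement so far).
- **Mixed (1):** Planning, which asks about steps taken or intended.

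Shares: 16/30 = 53% future only; 11/30 = 37% present; 2/30 = 7% to date, or 3/30 = 10% with the mixed question.

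**Sensitivity to judgement.** The two Self-efficacy items are the closest calls. Classing the first as present gives 15/30 = 50% future only. Classing the second as future instead gives 17/30 = 57%. The number asking what has happened stays at 2, or 3 with Planning.

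**Questions on barriers.** Only one main question uses the word, Patient Needs & Resources 3, and it is in the future tense. It concerns barriers to patients taking part. No main question asks which barriers or facilitators were met during implementation.

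**Probes.** These point both ways. Leadership Engagement 1 asks what support has been given, with examples, and Available Resources 1 asks about resources received or wished for. Against that, Compatibility 2, a present-tense question, has a probe on complications that may arise, and Leadership Engagement 1 also asks whether leaders know that implementation is intended.

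**The case against.** The strongest reply is that the guide is not a fixed questionnaire. The interview is semi-structured, its introduction tells respondents that their experience is wanted, and an interviewer speaking to someone who has delivered the tool would probably adjust the tense. Fourteen of the 30 main questions (30 − 16) are not future-only. Answers to the 11 present-tense ones, on matters such as complexity and fit with workflow, would be informed by use with at least 15 AYAs. The outcome is defined as perceived determinants by CFIR construct, so working through the constructs suits it, and the analysis admits emergent themes.

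Some forward-looking wording is also defensible. At the 15-AYA minimum, 15/50 = 30% to 15/25 = 60% of the planned sample would have been reached, so delivery may be continuing. The implementation guidance in Appendix A tells sites to use pilot testing to tailor the tool, and asking which changes are still needed serves that.

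Most of this stands, and it limits the consequence. It does not remove the mismatch. Leaving tense to improvisation may make answers differ between interviews, and a continuing pilot does not explain why barriers already met are never asked about directly.

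Three stronger readings are tempting and are not supported:

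- A reader might infer that Aim 1 would record forecasts in place of real determinants. The 14 other main questions and the experience probes rule that out.
- A reader might infer that this is a pre-implementation guide used unchanged. The wording suggests it, but the documents do not say so.
- A reader might infer that forecasts will be presented to Aim 3 interviewees as pilot findings. The documents say only that pilot data, and progress on implementation and outcomes, will be reviewed with them.

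**Conclusion.** The point holds as a mismatch between the interview's purpose and its questions. A postintervention interview with a retrospective introduction has 16 of 30 main questions (53%; 50% to 57% on the closest classifications) worded only about the future. Only 2 ask what has happened, or 3 with Planning, and none directly asks which barriers or facilitators were met. As written, the guide would mainly elicit expectations and current views, which weakens the only listed source for implementation determinants.

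This rests on classing main questions by their wording and on the guide being used broadly as written. An interviewer who consistently asked for experience would reduce the effect. The fidelity checklist and the AYA ratings of feasibility, acceptability and appropriateness come from other instruments and are untouched. The change is worth making before the provider interviews begin; it does not call the pilot design into question.

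**What to change.** Reword the prospective questions in Appendix D, with their prompts, to ask what happened in the pilot. Examples: which changes were made and why; what costs arose; what barriers AYAs faced in completing the assessment or taking up referrals; which resources were sufficient and which were lacking; how infrastructure helped or hindered.

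Add one direct open question asking which barriers and facilitators the provider met while implementing AYA NA-SB. Changing tense alone would not supply it.

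Forward-looking questions on continued use or tailoring can stay, with no need to cap their number, provided they are labelled as such. State in the Analytical Plan that their answers are coded as anticipated determinants, separately from experienced ones.

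The cost is an edit to Appendix D, a sentence on coding, and a minor IRB amendment. Interview length is essentially unchanged.

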Appendix E: Aim 3 Interview guide

Introduction:

Thank you for your interest in this study. The aim of the interview is to help us prepare for the future scale-up and sustainability of the AYA Needs Assessment and Service Bridge (NA-SB), and intervention that we developed to assess and address the needs of AYAs with cancer. During the interview, I will ask questions about how NA-SB might be implemented and sustained in your health system.

Our discussion should last approximately 30 minutes. Your responses will help us understand how NA-SB components or its implementation might need to be modified to address the needs of diverse health systems. All of your responses will remain confidential and will only be reported in aggregate. You may choose to stop the interview at any time, and there is no penalty to you or your organization for not completing the interview. Before we begin, we would like to ask your permission to audio record our discussion for the purposes of future analysis. Would it be OK with you if I record this interview? (If participant refuses to be audio-recorded, the RA will take notes instead.) The interview will be transcribed; however, your name or any personal identifiers will not be associated with any of the notes. The audio recordings will be deleted once the project is complete.

Do you have any questions before we begin?

YEAR ONE: Exploration

[Summarize progress of NA-SB implementation and outcomes in the North Carolina Cancer Hospital (NCCH), as it relates to the Exploration stage.]

I'd like to begin by discussing how AYAs' needs are assessed and addressed at your institution.

1. What happens when an AYA is diagnosed at your institution?

Prompts: How are new AYA patients identified? How are their needs identified and addressed? Are any formalized needs assessments or other tools used? Is a referral to a provider with AYA expertise automatically triggered?

2. Considering what I've told you about NA-SB's implementation and outcomes so far at NCCH, What are your thoughts on the appropriateness (&acceptability & feasibility) of NA-SB in the context of your health system? How do you see this as an opportunity? If not, what are the challenges in your health system that might influence the implementation of this intervention?

YEAR TWO: Preparation & Implementation

[Summarize progress of NA-SB implementation and outcomes at NCCH to date, as it relates to the Preparation & Implementation stage.]

I'd like to start by talking about the potential barriers/facilitators as you consider what preparing for the implementation of NA-SB might involve in your health system.

- 1. What activities might be pursued in your health system in preparation to implement NA-SB?
 - Examples: Training, financing, hiring, reorganizing, obtaining other resources, de-implementing previous approaches
 - Other prompts: whether these activities relate to different patient population / care setting and delivery / policy context / external environment associated with their health system
- 2. Are there particular barriers or facilitators that you have in mind as you think through how you would prepare to implement NA-SB?
 - Probe on why the participants perceive them as barriers or facilitators
 - Other prompts: patient population / care setting and delivery / policy context / external environment
 - E.g., how did your health system respond to changes (new practices or interventions), if any?

3. As you consider the experience of NCCH as I've described it, how do you think implementation might compare in your health system?

Prompts: Previous experience of implementing a new practice/intervention into the system?

4. How would the organization/health system proceed if they were to implement this new intervention?

Prompts: What are some next immediate steps? How would the organization determine who is in charge of what task? How does this differ from NCCH's experience? How? Why?

YEAR THREE: Sustainment

[Summarize progress of NA-SB implementation and outcomes at NCCH to date, as it relates to the Sustainment stage.]

- 1. How would your health system approach sustaining NA-SB?
- 2. What do you think the organization could do prior to implementation and/or during implementation to make it sustainable?

Prompts: When should the organization start thinking about sustainment? What process do you think is necessary? What resources do you think are needed to make this intervention sustainable?

Those are all of the questions that I had planned for today. Is there anything else that you want to share regarding the intervention or its scalability?

Thank you so much for your time!

